#### Interim analysis at the end of the 2-year study period

The study investigators agree with collaborators from Siemens and Bayer that an interim analysis at the end of the 2-year study period, of the proposed N=2,200, will inform the magnitude of the risk reduction rate. We firmly believe that the current proposed study of N=2,200 will lead to important and publishable results and we plan to publish manuscripts based on results obtained from the cohort of 2,200 patient subjects. However, this interim analysis will help to infer towards the planning of future studies and preparation of manuscripts that will provide key additional evidence regarding the clinical impact of stress CMR in the US. These actions include the possibility of proposing another study aiming at a larger sample size.

### **Specific Aim 2 – Assessment of the impact of CMR-guided invasive coronary revascularization, compared with medical therapy, on primary outcomes**

Sub-aim 2.1 Using a propensity score-matching analysis, test the hypothesis that in real-world clinical practice that stress CMR perfusion imaging-guided use of invasive coronary revascularization (INT) (defined by INT performed within 60 days after CMR) offers *AMI-free, coronary revascularization-free, survival benefits* over medical therapy (MED) in patients with suspected ischemia. We will estimate the # lives saved per 100 patients treated with INT versus MED (based on predicted primary outcome rate amongst MED)–(predicted primary outcome rate amongst INT)

Sub-aim 2.2 Using a propensity score-matching analysis, test the hypothesis that in real-world clinical practice that stress CMR perfusion imaging-guided use of INT offers *survival benefits free of primary or secondary outcomes* over MED in patients with suspected ischemia.

Sub-aim 2.3 The preferred initial treatment for patients with stable ischemic heart disease (SIHD) is the best available medical therapy. The benefits of using physiologic ischemia-based guidance to performing INT has been shown in the FAME and FAME-2 trials where fraction-flow-reserve was used to assess physiological significance of coronary stenosis. In FAME (multi-vessel SIHD) and FAME 2 (single or multi-vessel SIHD) trials: a 29% and 66% relative risk reduction of primary outcome at 2-years were reported, respectively. CMR perfusion assessment had demonstrated remarkable correlation to FFR based assessment of coronary physiologic significance. For sub-aim 2.3, test the hypothesis that comparing to the FAME-2 primary outcome rate of patients managed by medical management alone, CMR-guided INT patients have a relative risk reduction of 2-year primary outcomes  $\geq 30\%$ .

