## Sample Size

### For sub-aim 1:

The rate of cardiac hard events (death and acute MI) is estimated based on reported evidence of 0.5% and 6% per year for patients who have absence and presence of ischemia on CMR perfusion imaging, respectively. We plan to collect follow-up events for a 4-year period after CMR. Based on prior evidence, prevalence of ischemia on CMR perfusion was 23% in referred patients.

With a sample size of 2,200 patients, 506 (23%) are assumed to be with presence of ischemia and 1694 (77%) with absence of ischemia. With incidences of 6% and 0.5% per year and a 4-year follow-up, a total of 124 of 506 patients with ischemia and 36 of 1694 patients with no ischemia are expected to experience an event, i.e. a total of 150 patients with event.

A sample size of 2,200 patients overall and 150 patients with event in a 4-year follow-up is regarded sufficient to run multivariable analysis with up to 10 variables.

With regards to the sample size considerations on the time-to-event analysis, the following settings and assumptions were used:

- Power = 80%
- Level of significance (two-sided) = 5%
- Assumed proportion in control group (i.e. no revascularization) = 77%
- Total sample size = 2,200 patients
- Number of events = 150 in total sample
- 4-year follow-up for all patients available
- The hazard ratio is estimated by a Cox proportional hazard model

With a sample size of 2,200 patients and an event rate of 124 in group 1 and 36 in group 2, a hazard ratio of 0.59 can be detected with the above mentioned settings and assumptions (i.e. 41% risk reduction rate).

For sub-aim 2.3 (comparison to the historical FAME 2 study

As reported in published data (own BWH dataset and [name] et al Circulation 2011 Apr 12;123(14):1509-18), the event rate of patients who underwent revascularization guided by CMR ischemia (i.e. CMR physiologic guidance) is about 5% per year, i.e. 10% in a 2-year follow-up. In the

historic fame-2 study, the 2-year event rate of patients who did not use physiological guidance (N=441), was 19.5%. With a power of 80%, a two-sided alpha of 5% and an assumed difference under H1 of -9.5%, the sample size of patients in this registry needs to be at least 180 patients.

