### **Specific aim 2 (2 separate analyses for sub-aims 2.1 and 2.2, respectively)**

We structured the present study's analysis of observational data to mimic a randomized clinical trial: a patient's assignment to a treatment was based on the therapy selected in the first 60 days after stress CMR perfusion study and nonrandomized treatment adjusted for via a propensity score. This time point of 60 days was selected from previous work indicating that revascularization performed within this timeframe resulted from the noninvasive imaging study, whereas referrals after 60 days tended to be attributable to worsening clinical status. Based on our pilot data, approximately 10-15% of patients undergo early coronary revascularization within the first 60 days after CMR. We therefore anticipate that 85-90% of the study cohort received MED whereas 10-15% received INT.

We plan to examine the assumptions of proportional hazards in each of the Cox models. In addition, performance of the propensity score model will be tested by comparing the prognostic associations between treatment and clinical outcomes, without and with that propensity score matching. Key risk markers will be compared between the treatment groups, without and with inclusion of the propensity score matching.

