**Step 1: Propensity Score to Treatment** We plan to structure the study analysis of observational data in SA1 to mimic a randomized clinical trial: a) assignment of coronary intervention (INT) vs. medical therapy (MED) is based on the therapy selected in the initial 60 days after imaging and b) nonrandomized treatment adjusted for via a propensity score. Either PCI or CABG will define coronary revascularization. Follow-up time begins at the time of the index stress CMR imaging. To adjust for non-randomization of treatment, a single propensity score will be developed using logistic regression to model the decision to refer to revascularization considering all factors known to influence the referral decision. This single composite propensity score represents the probability of treatment assignment, which will be included in all subsequent survival models (step 2) associating stress CMR perfusion guided-treatment with the respective endpoints in each of the 3 sub-aims. This adjustment reduces the bias introduced by nonrandomized referral to INT in practice. While all factors known to influence this referral decision will be considered for entry into this logistic regression model, based on existing literature, the most likely predictors of referral to INT include % ischemic myocardium (% myocardial mass based on number of segments, by CMR), typical angina symptoms (yes if positive response to 2 of 3 Diamond and Forrester qualities, else no), infarct size (LGE size, grams of myocardial mass), ischemic ST changes on rest ECG (yes/no), pre-test coronary disease probability (ordinal), and prior cardiac catheterization (yes/no). We anticipate that 10-15% of patients (~n=300) received INT so model over-fitting will not occur when constructing this logistic regression model.

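### Sub-aim 2.3 takes CMR-guided INT to be any revascularization within 60 days, whatever the CMR showed, although it is motivated by and sized on INT guided by CMR ischemia

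*Combined protocol and SAP*

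**What the plan says.** Sub-aim 2.1, under Specific Aim 2, introduces CMR-guided INT and gives its only definition: "defined by INT performed within 60 days after CMR". Step 1 of the Specific aim 2 analysis repeats the rule. Assignment to INT or medical therapy (MED) "is based on the therapy selected in the initial 60 days after imaging", and "Either PCI or CABG will define coronary revascularization". The same section justifies the window by earlier work indicating that "revascularization performed within this timeframe resulted from the noninvasive imaging study". None of these places makes ischemia on the index CMR a condition.

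Sub-aim 2.3 uses the same term, CMR-guided INT, and tests for a relative reduction of at least 30% in two-year primary outcomes against the medically managed patients of FAME-2. Its rationale is the benefit seen when revascularization is steered by physiologic evidence of ischemia. Its paragraph under Sample Size takes the expected rate from "patients who underwent revascularization guided by CMR ischemia (i.e. CMR physiologic guidance) is about 5% per year, i.e. 10% in a 2-year follow-up". The comparator there is "patients who did not use physiological guidance (N=441), was 19.5" percent at two years. The stated minimum is 180 registry patients.

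**The concern.** The rule that selects patients and the population behind the hypothesis and its sizing are not the same. A patient revascularized on day 40 after a CMR without ischemia counts as CMR-guided INT under the rule, but does not belong to the group whose 5% per year the sizing uses. The plan allows for such patients. Step 1 lists typical angina, infarct size, ST changes on the rest ECG, pre-test probability and prior catheterization as likely drivers of referral to INT, alongside ischemia.

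Sub-aims 2.1 and 2.2 compare patients within the registry and adjust for percent ischemic myocardium. Sub-aim 2.3 compares registry INT patients with one published rate, and the analysis section describes no test, restriction or adjustment for it. The mix of ischemic and non-ischemic INT patients therefore passes straight into the estimated reduction. At stake are what that reduction describes and, in some circumstances, whether it reaches 30%.

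**Working it through.** **Inputs from the plan**
- Comparator two-year rate 19.5%, N = 441; planned INT two-year rate 10% (Sample Size, sub-aim 2.3).
- Success: relative risk reduction (RRR) of at least 30% (sub-aim 2.3).
- INT share 10-15% of 2,200, i.e. 220-330 patients (Statistical Analyses, Specific aim 2).

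**Inputs not in the plan (assumptions)**
- w, the share of INT patients without CMR ischemia.
- q, their two-year primary-outcome rate, taken as 1-5%. The lower end is the plan's 0.5% per year over two years. That figure covers death and AMI only, in all patients without ischemia, so it is no estimate for those who were revascularized.

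**1. The plan's 180.** For 10% v 19.5%, with 441 comparators fixed, 80% power and two-sided 5%, the pooled normal test needs 154 INT patients, or 172 with continuity correction. The stated 180 is not reproduced, but it is on the safe side: power at 180 is about 85% (pooled).

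**2. Threshold.** RRR = 1 - rate/19.5%. An RRR of 30% corresponds to 0.70 x 19.5% = 13.65%. At the planned 10%, RRR = 1 - 10/19.5 = 48.7%, so the threshold is met with no dilution.

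**3. Effect of mixing.** With p the ischemia-guided INT rate, the observed rate is (1 - w)p + wq, and RRR changes by w(p - q)/19.5%. For w = 10%:

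| p | q = 1% | q = 5% |
|---|---|---|
| 10% | 0.9/19.5 = +4.6 points | 0.5/19.5 = +2.6 points |
| 15% | 1.4/19.5 = +7.2 points | 1.0/19.5 = +5.1 points |

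The sign is that of p - q. If q equals p there is no bias; if q exceeds p the reduction is understated.

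**4. Share needed to cross 30%.** When p is above 13.65%, w* = (p - 13.65%)/(p - q).

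| p | True RRR | w* (q = 1% to 5%) |
|---|---|---|
| 14% | 28% | 3-4% |
| 15% | 23% | 10-14% |
| 16% | 18% | 16-21% |
| 18% | 8% | 26-34% |
| 19.5% | 0% | 32-40% |

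**5. Example.** Take p = 15% (true RRR 23%) and w = 20%. With q = 1% the mixed rate is 0.8 x 15 + 0.2 x 1 = 12.2%, an apparent RRR of 37%. With q = 5% it is 13.0%, or 33%. With 300 INT patients, an observed RRR of at least 30% against a fixed 19.5% means at most 40 events (13.65% x 300 = 40.95). The binomial chance of that is 24% with no mixing, 76% with q = 1% and 61% with q = 5%. If w is only 5%, q = 1% gives 14.3% and an RRR of 27%, which does not cross.

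**6. Size of a restricted group.** If 20% of INT patients had no ischemia, 0.8 x 220 = 176 to 0.8 x 330 = 264 remain. The low end is just under 180 but above 154 and 172. With 220 INT patients, the group falls below 154 only if the share exceeds 30% (0.70 x 220 = 154).

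**The case against.** The timing rule is a reasoned choice: the plan cites earlier work attributing revascularization in the window to the imaging study, and Aim 2 addresses real-world practice in patients with suspected ischemia. Sub-aim 2.3 could also be read as already limited to ischemia-guided INT, given its rationale and sizing text. Step 1 says the propensity score will be used in all three sub-aims. And on the plan's own 10% rate the result does not turn on this point.

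The last argument stands, and it limits the consequence. The others do not close the gap. Attributing a procedure to the imaging study does not require that the study was positive. The limited reading of sub-aim 2.3 conflicts with the only definition given, so an analyst following the text would include everyone revascularized within 60 days. A propensity score built within the registry does not by itself align INT patients with an external published rate.

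A reader might also infer that sub-aims 2.1 and 2.2 need the same restriction. The documents do not support that: percent ischemic myocardium is a likely propensity predictor and a named Cox covariate, and treatment-by-covariate interactions are planned. Limiting those comparisons to proven ischemia would change the question they ask.

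**Conclusion.** The mismatch between definition and sizing is in the text, and it matters for sub-aim 2.3, where no adjustment is described. The size and direction of any bias are unknown, because the plan gives neither the share nor the event rate of INT patients without CMR ischemia. If their two-year rate is 1-5%, each tenth of the INT group they make up inflates the reduction by about 3-5 points (ischemia-guided rate 10%) or 5-7 points (15%).

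A reader might infer that low-risk patients will carry sub-aim 2.3 over its threshold, or that such patients have the plan's 0.5% per year risk. Neither follows. That rate omits late revascularization, which is part of the primary outcome, and describes all patients without ischemia; those sent to PCI or CABG despite a negative CMR are a selected group who may be at higher risk. Pass or fail changes only if the ischemia-guided rate is above 13.65%, against a planned 10%, and the share is large enough: about 10-14% or more at a rate of 15%. The point merits correction because the claim concerns ischemia-guided treatment and the remedy is cheap.

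**What to change.** For sub-aim 2.3:
- Define the primary analysis set as patients with INT within 60 days after an index CMR showing ischemia.
- Report INT counts and two-year event rates by ischemia status.
- Keep all 60-day INT as a sensitivity analysis.
- Reconcile the definition in Specific Aim 2 and Step 1 with the population named under Sample Size.

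Leave the primary analyses of sub-aims 2.1 and 2.2 as planned. A version restricted to patients with ischemia can be added there as a sensitivity analysis.

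The cost is wording in the analysis plan: presence of ischemia is already needed for Specific Aim 1, and segmental perfusion is collected. The downside is a somewhat smaller 2.3 group, which may fall just under the stated 180. The revised text should acknowledge this and give the recomputed requirement.

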## Study Endpoints and Hypotheses to Test

### Study Endpoints

Primary outcomes include all-cause mortality, acute myocardial infarction (AMI), and late coronary revascularization (PCI or CABG beyond 60 days after CMR).

Secondary outcomes include non-fatal cardiac events (including cardiac hospitalizations for unstable angina or heart failure, heart transplant, significant ventricular arrhythmias, and strokes), alteration of diagnostic and therapeutic decision, and cardiac event-weighted QALY.

The specific aims of this project are listed below:

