#### **c) Clinical Outcomes within 4 years after CMR**

Primary outcomes: a) All-cause including cardiac mortality, b) new acute MI, within 4 years after CMR imaging, and c) late coronary revascularization (PCI or CABG beyond 60 days after CMR);

Secondary outcomes: heart failure hospitalization, unstable angina hospitalization, heart transplantation, significant ventricular arrhythmias, and strokes, within 4 years after CMR. Times to all of the above events will be collected. Other supportive data: angiographic reports including PCI details, CABG operative reports. Repeat events of all non-fatal outcomes will be collected using our web-based data structures (Appendix A4).

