**Step 2: Multivariable survival analyses for treatment's impact incorporating the propensity score (sub-aims 2.1 and 2.2).** A Cox proportional hazards model will be used to assess the association of treatment with the primary outcome (sub-aim 2.1) and secondary outcome-free survival (sub-aim 2.2). For each of sub-aim 2.1 and 2.2, we plan to build a survival model using Cox proportional hazards regression to control for the effects of baseline patient differences. Key known risk markers to be included in these models are age, sex, diabetes, and % ischemic myocardium. Major Treatment (INT or MED) and the propensity score will then be entered into the model to assess for any survival advantage from INT vs MED adjusting for the nonrandomized referral pattern. Any potential impact by any covariate in the model onto the survival benefit from INT, will be tested by adding an interaction term between treatment and the covariate of interest.

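### Sub-aim 2.1 computes lives saved per 100 patients from the three-part primary outcome, so the figure counts primary-outcome events avoided, not deaths avoided

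*Combined protocol and SAP*

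**What the plan says.** Specific Aim 2, sub-aim 2.1, sets out the estimate: "We will estimate the # lives saved per 100 patients treated with INT versus MED (based on predicted primary outcome rate amongst MED". The second term, which is subtracted, is the "predicted primary outcome rate amongst INT".

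The primary outcome is defined twice, with the same three components:
- Study Endpoints: "Primary outcomes include all-cause mortality, acute myocardial infarction (AMI), and late coronary revascularization (PCI or CABG beyond 60 days after CMR".
- Data to Collect, item c: "Primary outcomes: a) All-cause including cardiac mortality, b) new acute MI, within 4 years after CMR imaging, and c) late coronary revascularization".

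Statistical Analyses, Specific aim 2, Step 2, names one model for this sub-aim: "A Cox proportional hazards model will be used to assess the association of treatment with the primary outcome (sub-aim 2.1". Neither that section nor Step 1 mentions the lives-saved figure, a mortality-only model or predicted mortality.

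On timing, sub-aim 2.1 gives no horizon for the predicted rates. Sub-aim 2.3 works at 2 years, and Data to Collect, item c, covers 4 years after CMR.

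**The concern.** The label and the formula describe different quantities. The label is about deaths; the formula subtracts rates of an outcome that also counts MI and revascularization after day 60. Treatment group is set by what happens in the first 60 days. A MED patient who has PCI on day 70 and survives all 4 years therefore enters the formula exactly as a death does, and so does an INT patient with a repeat PCI on day 70. Neither is a life lost.

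The figure is likely to be quoted. The Rationale section says the aims should supply core evidence for insurers' reimbursement decisions, and it lists mortality separately from non-fatal cardiac outcomes. A payer given lives saved per 100 would take it as a mortality effect, and the bare number would not show whether mortality differs at all.

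**Working it through.** The plan states no value for lives saved, so there is no figure to reproduce. The check is a comparison of definitions, followed by the size of the gap and the precision of the alternative.

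**1. What the formula measures.** At any time t after CMR:

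P(primary outcome by t) = P(dead by t) + P(alive at t with a prior AMI or late revascularization)

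Taking MED minus INT on both sides:

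composite difference = lives saved + D

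Here D is the MED minus INT difference in the proportion alive at t after a non-fatal primary event. The label is correct only if D = 0. D can have either sign, because AMI and late revascularization count in both arms.

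**2. Can D be sized from the documents?** No. The hard-event rates in the Sample Size section combine two components: "The rate of cardiac hard events (death and acute MI) is estimated based on reported evidence of 0.5% and 6% per year". No rate for death alone is given anywhere.

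**3. Illustration of scale only.** The Sample Size section uses 2-year event rates of 19.5% and 10% for sub-aim 2.3. These compare registry patients with an external study and are not expected results for sub-aim 2.1. Put into the formula:

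100 × (0.195 − 0.10) = 9.5 per 100

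Lives saved would then be 9.5 − D, with D per 100:

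| Assumed D per 100 | Lives saved per 100 |
|---|---|
| 0 | 9.5 |
| 4.75 | 4.75 |
| 9.5 | 0 |

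A negative D gives more than 9.5 lives; a D above 9.5 gives excess deaths under INT. The same reported figure fits all of these.

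**4. Precision of a true mortality estimate.** Statistical Analyses, Step 1, gives the INT group size: "We anticipate that 10-15% of patients (~n=300) received INT". Assumptions: equal risk p in both groups, simple binomial variance, and 4-year mortality p of 2%, 5% or 10%, since the documents give none. The plan speaks of propensity matching but states no ratio, and Steps 1 and 2 enter the score as a covariate, so two layouts are shown: 300 vs 300 (1:1 matching) and 300 vs 1,900 (2,200 − 300, whole cohort).

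Half-width of the 95% CI per 100 = 100 × 1.96 × √[p(1−p)(1/n₁ + 1/n₂)]

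Hazard-ratio CI factor = exp{1.96 × √[1/(n₁p) + 1/(n₂p)]}

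| p | Deaths among 300 | Half-width, 300 vs 300 | HR factor, 300 vs 300 | Half-width, 300 vs 1,900 | HR factor, 300 vs 1,900 |
|---|---|---|---|---|---|
| 2% | 6 | 2.24 | 3.10 | 1.7 | 2.4 |
| 5% | 15 | 3.49 | 2.05 | 2.7 | 1.7 |
| 10% | 30 | 4.80 | 1.66 | 3.7 | 1.5 |

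For example, at p = 5% with 300 vs 300: 100 × 1.96 × √(2 × 0.05 × 0.95 / 300) = 3.49, and exp(1.96 × √(2/15)) = 2.05. The whole-cohort columns are optimistic where propensity scores overlap poorly.

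**The case against.** The best defence is that this is loose wording in an aims paragraph. The phrase appears once, the analysis section does not carry it forward, and no test, sample size or decision rule depends on it. The formula is printed beside the label, so a reader of the protocol can see what is subtracted. This limits the weight of the point but does not remove it: the formula is explicit, nothing elsewhere corrects the label, and a published figure would travel without the formula.

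The Study Endpoints section also never uses the word composite. However, sub-aim 2.1 tests survival free of both AMI and revascularization, and Step 2 models one primary outcome, so the combined reading is clear.

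On the time point, 4 years is the natural reading: outcomes are collected over 4 years, the Sample Size section assumes 4-year follow-up for all, and the 2-year horizon belongs to the external comparison in sub-aim 2.3. That is fair, but an absolute risk difference needs its horizon stated, and here it is only inferred.

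Finally, the precision figures depend on a layout the plan does not fix. That stands, which is why both layouts are shown. They describe the cost of one remedy and are not evidence for the mismatch.

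**Conclusion.** The concern holds. As written, sub-aim 2.1 yields the difference in the proportion of patients with a first death, AMI or late revascularization, and calls it lives saved. The conclusion rests on the documents' own definitions and needs no numerical assumption. The size and direction of the error cannot be stated, because the documents contain no mortality rate.

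The sub-aim 2.1 hypothesis test on the primary outcome is untouched. What is wrong is the labelled absolute-effect estimate, and it should be corrected before any result is reported under that name.

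**What to change.** **Minimum change.** In sub-aim 2.1, rename the figure as (first) primary-outcome events avoided per 100 patients and state the time point, for example 4 years to match Data to Collect, item c. This is one line of text and cures the mismatch by itself.

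**Useful addition.** Report the difference by component: all-cause death, AMI and late revascularization. The death line should count every death by the time point, including deaths after a non-fatal event; a split by type of first event would miss those.

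**If lives saved is kept.** Compute it as propensity-adjusted all-cause mortality, MED minus INT, at the stated time, with a 95% CI, and add this to Statistical Analyses, Specific aim 2, Step 2. It needs one extra model and no new data: for the listed outcomes, "Times to all of the above events will be collected", and the Appendix A4 form records date of death and date last known alive. The cost is precision. In the 1:1 layout the interval would be about ±2.2 to ±4.8 lives per 100 over the assumed 2% to 10% mortality, so the estimate may well be inconclusive and should be presented as such. If that is not acceptable, use the renamed composite figure alone.

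### The sub-aim 2.1 benefit-per-100 formula names no common population or time point; applied group by group to the Step 2 Cox model, it would undo the adjustment and could reverse the sign

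*Combined protocol and SAP*

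**What the plan says.** Sub-aim 2.1 (Specific Aim 2) begins "Using a propensity score-matching analysis, test the hypothesis" and then defines the benefit per 100 patients as "based on predicted primary outcome rate amongst MED)–(predicted primary outcome rate amongst INT". It gives no averaging population and no time point.

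The introduction to Specific aim 2 under Statistical Analyses also speaks of matching: "Key risk markers will be compared between the treatment groups, without and with inclusion of the propensity score matching".

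The operative steps do something else. Step 1 fits one logistic propensity score, "which will be included in all subsequent survival models (step 2". Step 2 is a Cox model: "Key known risk markers to be included in these models are age, sex, diabetes, and % ischemic myocardium", after which "Major Treatment (INT or MED) and the propensity score will then be entered into the model". Neither step gives a matching ratio, caliper, replacement rule or matched population.

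Step 1 also says how the two groups will differ: "the most likely predictors of referral to INT include % ischemic myocardium", followed by angina, infarct size and other factors.

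**The concern.** The phrases for the two rates, read literally, describe predictions in two observed groups. By the plan's own account these groups differ in ischemic burden, which is also expected to drive outcome. A Cox model with the propensity score adjusts the hazard ratio. That adjustment reaches the absolute difference only if both predictions use the same patients. Averaging each group's predictions over its own covariates puts the case-mix difference back.

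The per-100 figure is the only absolute effect measure stated for sub-aim 2.1. The Rationale section says that the three aims together are meant to inform reimbursement decisions. Under the present wording, two competent analysts could report opposite signs from the same fitted model, and each could claim to have followed the plan.

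**Working it through.** The plan gives no value for the benefit per 100, so there is no stated figure to reproduce.

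**1. Why group-wise averaging returns the crude difference.** In a Cox model with a binary treatment term, the score equation for that term makes observed minus model-expected events sum to zero over INT patients. With the usual (Breslow) baseline the same sum is zero over the whole cohort, and so over MED patients too. Each group's predictions are therefore calibrated to that group's own events. Subtracting the group averages approximately gives the crude difference, whatever the adjusted hazard ratio is.

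A simulation shows the size: 200 replicates, N = 2,200, the Sample Size event rates, INT about 12.8%, an assumed true hazard ratio of 0.70, and a Cox model with treatment, age, % ischemia and propensity score.

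| Quantity | Mean |
|---|---|
| Adjusted hazard ratio | 0.71 |
| MED minus INT at 2 years, each group's own covariates | -7.2 per 100 |
| Crude MED minus INT at 2 years | -7.2 per 100 |
| INT patients predicted under both treatments, 2 years | +3.8 per 100 |

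**2. Illustration with the planning rates.** Inputs from Sample Size:
- 2,200 patients, of whom 0.23 × 2,200 = 506 are ischemic and 1,694 are not.
- 6% per year with ischemia and 0.5% per year without.
- For INT, "the event rate of patients who underwent revascularization guided by CMR ischemia (i.e. CMR physiologic guidance) is about 5% per year".

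The introduction to Specific aim 2 gives an INT share of 10-15%, so k = 220, 275 or 330 INT patients.

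Assumptions that are not in the plan: the rates are treated as one endpoint, hazards are constant, and all INT patients are ischemic.

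Risk at h years = 1 - exp(-h × rate). For INT at 2 years, 1 - exp(-0.10) = 9.52%. (The plan doubles 5% to get 10%.)

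The 6% can be read in two ways.

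*Reading A: 6% applies to ischemic MED patients.* MED rate = [(506 - k) × 6 + 1,694 × 0.5] / (2,200 - k). At k = 275: (1,386 + 847) / 1,925 = 1.16% per year.

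*Reading B: 6% is the average over all ischemic patients, INT included.* Ischemic MED rate = (506 × 6 - k × 5) / (506 - k). At k = 275: (3,036 - 1,375) / 231 = 7.19% per year. Overall rate = 0.23 × 6 + 0.77 × 0.5 = 1.765% per year. With p the INT share, MED rate = (1.765 - p × 5) / (1 - p). At p = 0.125 this is 1.30% per year.

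| INT share | MED rate/yr, A / B | Formula, unmatched, 2 yr, A / B | Ischemic MED rate/yr, A / B | Ischemic MED minus INT, 2 yr, A / B |
|---|---|---|---|---|
| 10% | 1.29 / 1.41 | -6.96 / -6.74 | 6.00 / 6.77 | +1.79 / +3.15 |
| 12.5% | 1.16 / 1.30 | -7.22 / -6.94 | 6.00 / 7.19 | +1.79 / +3.88 |
| 15% | 1.02 / 1.19 | -7.50 / -7.16 | 6.00 / 7.88 | +1.79 / +5.06 |

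Rates are in percent and differences are per 100 patients. At 4 years the unmatched formula gives -12.7 to -14.1, against +3.2 to +8.9 in ischemic patients. If only 80-90% of INT patients are ischemic, the signs stay the same. Over all these scenarios the annual difference is -3.5 to -4.0 per 100 unmatched and +1.0 to +2.9 in ischemic patients.

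**3. Whether matching can simply be assumed.** If all INT patients are ischemic, the ischemic MED patients available as matches number 506 - k = 286, 231 and 176, for 220, 275 and 330 INT patients. Full 1:1 matching on ischemia without replacement fails once k exceeds 506 / 2 = 253, an INT share of 253 / 2,200 = 11.5%. That lies inside the planned 10-15%. The matched population therefore has to be defined before it can serve as the target.

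**The case against.** The strongest reply is that matching is specified, in the sub-aim itself and again in the introduction to the Specific aim 2 analysis. In a matched set the two groups would be balanced on measured factors, and MED minus INT would be a sound subtraction. Because the formula uses predicted rather than observed rates, it also leaves room for predictions at common covariate values, in which case the sign follows the adjusted hazard ratio. The hypothesis in sub-aim 2.1 is tested through the treatment term in Step 2, which the formula does not touch.

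All of this stands as a limit on the point. A reader might infer that the plan prescribes a crude subtraction, or that it will report harm where comparable patients benefit. The documents support neither reading:
- They leave the averaging population open. They do not state that it is each observed group.
- The 0.5% and 6% rates cover death and acute MI only and are split by ischemia, not by treatment. The primary outcome adds late revascularization.
- The 5% INT rate comes from the sub-aim 2.3 calculation, and its components are not stated.
- Sharing the label ischemic does not make patients comparable, because Step 1 expects several other factors to drive referral.

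Nor do the documents call the per-100 figure the main result for payers. The Rationale section speaks of the three aims together.

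The reply does not remove the gap. Steps 1 and 2 are the only executable instructions. They form no matched set, and nothing says that both predictions are for the same patients. Outcomes are collected within 4 years, but no horizon is tied to this figure.

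**Conclusion.** The point holds as a defect of definition with a material consequence. The formula has no stated population and no stated horizon, and the plan describes two different adjustment methods. One natural way of applying the formula to the Step 2 model undoes the adjustment and can give an absolute effect of the wrong sign.

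The mechanism does not depend on the planning rates; it needs only the case-mix difference that Step 1 anticipates. The size does depend on them. About -6.7 to -7.5 per 100 against +1.8 to +5.1 at 2 years is an illustration that rests on the pooled endpoint, constant hazards, all INT patients being ischemic, and either reading of the 6% rate. It is not evidence that INT helps or harms. The adjusted hazard ratio and its test are unaffected.

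**What to change.** In sub-aim 2.1, state that both rates refer to the same patients. From the Step 2 model, predict each patient's risk once with treatment set to INT and once with it set to MED. Average both over one named population (for example, the INT patients), and report MED minus INT at fixed horizons of 2 and 4 years with a bootstrap 95% confidence interval.

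Alternatively, compute both rates only in a matched set, and define that set in advance: ratio, caliper, replacement rule, and what happens to INT patients without a match.

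In either case, reconcile the matching wording in sub-aim 2.1 and in the introduction to the Specific aim 2 analysis with the covariate adjustment in Steps 1 and 2, so that one method is primary.

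The cost is a revision of the wording and a little analysis code. No new data are needed.
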